### 1. AMENDMENT HISTORY

Amendment No.	Protocol Version No.	Date issued	Author(s) of changes	Details of Changes made
1	1.2		[name]	Added sodium nitroprusside to the iontophoresis technique.
2	1.3		[name]	“participants who do not want their GP informed will be provided with the GP letter”

## 2. SYNOPSIS

Study Title	Beet the cold: The effect of inorganic nitrate supplementation on peripheral blood flow and pain in individuals with Raynaud's phenomenon. A pilot, double-blind, placebo controlled, randomised crossover trial.
Internal ref. no.	n/a
Problem statement	Raynaud's Phenomenon (RP) can cause significant discomfort and pain to individuals during a vasospasm. Dietary nitrate appears to offer a simple, low cost means of modifying blood flow to the peripheries and, ultimately, reducing both the discomfort and pain experienced by individuals with RP. This study will also advance our understanding of the aetiology and pathophysiology of RP, specifically the role that the nitrate-nitrite-nitric oxide pathway might play in modulating RP symptoms. An understanding of the effects of concentrated beetroot juice on microvascular blood flow and pain may lead to a range of simple, low cost and effective therapeutic interventions to prevent and treat episodes of RP.
Research question / hypothesis	Primary objectives: Does concentrated beetroot juice (CBJ) increase peripheral blood flow, improve endothelial function and increase skin temperature compared to placebo in people with RP. Secondary objectives: 1) Does CBJ reduce perceived discomfort and pain and, 2) is our protocol acceptable to individuals with RP (i.e. cold water stimulus, CBJ palatability) and feasible to perform in a future multi-centre randomised control trial (RCT) and, 3) to establish recruitment and retention rates. Resulting estimated effect size in relation to their confidence intervals from our primary objective(s) measures will be utilised to identify our primary outcome measure and to power a larger, definitive, multi-centre randomised, control trial.
Study Design	The proposed study will be a pilot, randomised placebo-controlled, double-blind, crossover trial.

[figure not shown]
Study Participants	Individuals with primary and secondary Raynaud's phenomenon.
Planned Sample Size	Twenty-five individuals with RP would need to be recruited in order to estimate a moderate to large effect size in a pilot study. Therefore, we aim to recruit 30 individuals (at a rate of 1 per week) to account for drop outs.
Follow-up duration	2 weeks
Planned Study Period	1 year
Primary Objective	Primary objectives: Does CBJ increase peripheral blood flow, improve endothelial function and increase skin temperature compared to placebo in people with RP.
Secondary Objectives	Secondary objectives: 1) Does CBJ reduce perceived discomfort and pain and, 2) is our protocol acceptable to individuals with RP (i.e. cold water stimulus, CBJ palatability) and feasible to perform in a future multi-centre randomised control trial (RCT) and, 3) to establish recruitment and retention rates. Resulting estimated effect size in relation to their confidence intervals from our primary objective(s) measures will be utilised to identify our primary outcome measure and to power a larger, definitive, multi-centre randomised, control trial.
Primary Endpoint	N/A: pilot study.
Secondary Endpoints	N/A: pilot study.
Intervention (s)	4 weeks of CBJ supplementation. 2 with nitrate rich CBJ and 2 weeks with nitrate depleted CBJ.

### 3. ABBREVIATIONS

Ach	= Acetylcholine
CBJ	= Concentrated beetroot juice
CRF	= Clinical records folder
eGFR	= Estimate of glomerular filtration rate
flux/MAP	= Cutaneous vascular conductance
FTE	= Full time equivalent
GTN	= Glyceryl trinitrate
NHS	= National Health Service
NO•	= Nitric oxide
PCPI	= Patient, carer and public involvement
RCT	= Randomised control trial
REC	= Research Ethics Committee
RP	= Raynaud 's phenomenon
SF-36	= Short Form Health Survey
TBC	= Total blood count

#### 4. BACKGROUND AND RATIONALE

Raynaud's phenomenon (RP) is characterised by a recurrent transient vasospasm of the fingers or toes in response to a cold or stressful stimulus (Wigley 2002). Nitric oxide (NO•) is a known vasodilator and NO• donors, such as Glyceryl Trinitrate (GTN), improve blood flow in patients with RP (Anderson et al., 2002; Teh et al., 1995) and in cold sensitive individuals (Hope, [name], Golden, & Tipton, 2014) (Figure 1, see accompanying document). However, individuals develop a tolerance to GTN and show diminishing vasodilatory effects with chronic treatment (Needleman & Johnson, 1973). In addition, the deleterious side effects such as headaches (Hsi, Rosenthal, Singh, Szombathy, & Meszaros, 2005; Wigley 2002) means that organic nitrates (i.e. GTN and isosorbide mononitrate) are not optimal long-term therapies for RP. Alternative treatments therefore, warrant further investigation.

**Figure 1.** Effect of GTN on foot skin temperature of cold sensitive individuals during a 2 min cold challenge test. (A) individual thermogram taken after 5 min of rewarming following a 2 min immersion in 15°C water with GTN and (B) with placebo (C) depicts mean toe temperature before during and after the cold challenge with placebo (closed circles) and GTN (open circles; n=6) (Hope et al., 2014).

Diets rich in fruit and vegetables have been shown to be effective in reducing blood pressure (Appel et al., 1997; Rouse, Beilin, Armstrong, & Vandongen, 1983). In addition, they lower the risk of morbidity and mortality from cardiovascular disease (Bazzano et al., 2001;

Joshipura et al., 1999; Joshipura et al., 2001) and are thought to be beneficial to cardiovascular health due to their vasodilatory effects (M [name], Winyard, & Benjamin, 2010). As diet exhibits such tremendous intra- and inter-individual variation, elucidating which components of such a diet are responsible for this effect is difficult. There is a growing weight of evidence from both human and animal studies that nitrate and nitrite derived from the diet can serve as a source for nitric oxide (NO; please see below), particularly where it is deficient (V. Kapil, Weitzberg, Lundberg, & Ahluwalia). Indeed, the greatest protective effect on cardiovascular disease is to be found in those diets with the greatest consumption of green leafy and or cruciferous vegetables (Joshipura et al., 1999; Joshipura et al., 2001) which typically have high nitrate content.

NO is produced in the body in two ways. The first requires the availability the amino acid L-arginine, molecular oxygen, and families of enzymes, the nitric oxide synthases ((NOS); (Moncada & Higgs, 1993; Moncada, Palmer, & Higgs, 1989)); that is the NOS pathway. The second pathway is independent of the NOS pathway and involves the stepwise enzymatic and chemical reduction of inorganic nitrate to nitrite (Benjamin et al., 1994; Björne et al., 2004; Lundberg, Weitzberg, & Gladwin, 2008; Zweier, Wang, Samouilov, & Kuppusamy, 1995). A major source of nitrite in humans is the reduction of dietary nitrate by facultative anaerobic bacteria in the mouth (Duncan et al., 1995). The remaining nitrite is then absorbed into the circulation where it acts as a storage pool for subsequent NO• production, which is expedited in hypoxaemia (Cosby et al., 2003).

Localised hypoxemia such as that observed in the digital vasculature of individuals with RP (Wigley 2002) is a potential therapeutic target for dietary nitrate supplementation. In contrast to organic nitrates (GTN), inorganic nitrate (in the form of beetroot juice) does not cause the same negative side effects (Anthony I. [name] et al., 2015) or demonstrate tachyphylaxis (Vanhatalo et al., 2010) whilst it does notably improve skin blood flow (Levitt, Keen, & Wong, 2015), microvascular function (Hobbs et al., 2013; Vikas Kapil, Khambata, Robertson, Caulfield, & Ahluwalia, 2015) and lower blood pressure (BP) in healthy individuals and chronic conditions such as hypertension (Vikas Kapil et al., 2015), peripheral arterial disease, (Kenjale et al., 2011) heart failure (Zamani et al., 2015) and chronic obstructive pulmonary disease (Berry et al., 2014). Thus concentrated beetroot juice (CBJ)

may offer an inexpensive, safe and potentially effective intervention to improve the pain and reduced peripheral blood flow characterising individuals with RP.

RP can cause significant discomfort and pain to individuals during a vasospasm. Dietary nitrate appears to offer a simple, low cost means of modifying blood flow to the peripheries and, ultimately, reducing both the discomfort and pain experienced by individuals with RP. This study will also advance our understanding of the aetiology and pathophysiology of RP, specifically the role that the nitrate-nitrite-nitric oxide pathway might play in modulating RP symptoms. An understanding of the effects of CBJ on microvascular blood flow and pain may lead to a range of simple, low cost and effective therapeutic interventions to prevent and treat episodes of RP.

The proposed study will be a pilot, randomised placebo-controlled, double-blind, crossover trial. The effect of acute (1 day) and chronic (2 weeks) CBJ supplementation on microvascular function (skin blood flow and speed of rewarming of the hand and foot) in people with RP will be compared to a placebo (CBJ with the nitrates removed). A summary of the main risks of this study include; a well-recognised side effect of beetroot consumption, is that it may turn urine and faeces red. This is not harmful and will pass rapidly after discontinuation of the juice. Subjects will be told of this during the consent visit. Intravenous access can cause discomfort associated with insertion of the needle. We will take a blood sample on three occasions. Some discomfort can be caused during iontophoresis (an itchy feeling) and some pain may be felt when immersing the hand and foot in to 15°C water for 2 minutes. Participants will be made aware that they can withdraw at any stage in accordance with GCP and informed consent.

## **5. PRELIMINARY STUDIES AND EXPERIENCE OF INVESTIGATORS**

Dr's [name], [name] and [name] are leaders in the field of nitrate supplementation (particularly beetroot) and have over 70 peer reviewed publications between them in the field. The Department of Sport and Exercise Science (DSES) at the University of Portsmouth (UoP) has a world leading environmental group. Dr's [name] and [name] from this group are leaders in this field and will be helping with controlling environmental conditions and the specific tests for this study (i.e. iontophoresis and cold sensitivity tests). [name] has extensive experience of running focus groups and performing qualitative research in patient groups.

Dr's [name] and [name] are clinicians with extensive experience of running clinical trials. See reference list for publications and attached CV's.

## 6. AIMS AND OBJECTIVES

The overall aim is to establish if this protocol is acceptable and feasible to perform whilst establishing effect sizes for our primary and secondary outcomes to power a larger definitive trial.

### 6.1 Primary Objective

Primary objectives: Does CBJ increase peripheral blood flow, improve endothelial function and increase skin temperature compared to placebo in people with RP.

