## 7.2 Primary and Secondary Endpoints/Outcome Measures

This is a pilot study and as such, primary outcome measures are N/A. See above for our primary and secondary objectives. These will be used to inform what our primary outcomes will be in a future trial.

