#### 10.4 Study Assessments

*Endothelial function test:* Following a 30 minute acclimatisation period, acetylcholine (ACh) and sodium nitroprusside will be delivered transdermally using iontophoresis to three sites, the middle phalanx of the middle finger of the left hand, the dorsal aspect of the left foot and the volar aspect of the left forearm. Cutaneous vascular conductance and skin temperature will be measured to determine the dose response to ACh at each site separately (Maley et al., 2015).

*Cold challenge test:* Following a 15 min acclimatisation period, participants will undertake light exercise on a cycle ergometer for 12 min (maximum of 50 W, to elevate their core temperature by approximately 0.3°C). Prior exercise has been found to increase the reproducibility of the test ([name] et al. 2005) by removing the effect of varying central vasoconstrictor tone. Participants will then undertake a standardised cold challenge test by immersing their hand and foot separately into 15°C water for 2 minutes followed by spontaneous rewarming for 10 minutes ([name] et al., 2013; Hope et al., 2014). Skin temperature (from a thermal imaging camera), peripheral (skin) blood flow (laser Doppler) thermal sensation, comfort and pain will be measured throughout the test.

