### 14.2 Analysis of Endpoints

All data will be tested for normality. Where data are not normally distributed a nonparametric test will be performed. Data will be presented as means  $\pm$  SD. Statistical analyses will be performed on SPSS software version 22.0 (Chicago, IL). Statistical difference will be accepted when  $P < 0.05$ . Statistical differences will be assessed by repeated-measures

ANOVAs. Where baseline differences are present, analyses of covariance (ANCOVAs) will be used with baseline as a covariate.

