#### 14.3 Procedure for Dealing with Missing, Unused and Spurious Data

Where statistic differences are present, post hoc (Bonferroni-corrected) analysis will be performed. Outliers will remain within the data. Within the data analysis software missing data will be coded 9999 and the data point missed during analysis.

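### The analysis section answers an efficacy question at P < 0.05 with no control across measures, and does not specify the effect sizes and confidence intervals the pilot is meant to deliver

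*Combined protocol and SAP*

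**What the plan says.** Section 6 sets the overall purpose: "The overall aim is to establish if this protocol is acceptable and feasible to perform", together with obtaining effect sizes to power a definitive trial. The synopsis and section 6.2 add that effect sizes, read with their confidence intervals, will be used to select the future primary outcome and size that trial. Section 20 repeats this.

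The primary objective in section 6.1 is a different kind of statement, a question about whether the juice works: "Does CBJ increase peripheral blood flow, improve endothelial function and increase skin temperature compared to placebo in people with RP". Section 6.2 words the discomfort and pain objective in the same way. Section 7.2 ranks no measure first: "This is a pilot study and as such, primary outcome measures are N/A".

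Section 14.2 supplies the only decision rule: "Statistical difference will be accepted when" P < 0.05. On method it says "Statistical differences will be assessed by repeated-measures" ANOVAs, with ANCOVA if baselines differ and a nonparametric test if data are not normal. Results are to be shown as means ± SD. The one multiplicity step is in section 14.3: "Where statistic differences are present, post hoc (Bonferroni-corrected) analysis will be performed". Section 14.4 says that no SAP is needed beyond this.

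**The concern.** The stated use of the pilot is estimation, but the analysis section describes significance testing. Two things follow.

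- The quantity the sponsor needs for the next trial, a CBJ-minus-placebo difference with its interval, is specified nowhere in section 14.
- Several measures are tested under one efficacy question, with no lead outcome, no adjustment across measures and no statement that the tests are exploratory. A single P < 0.05 could then be reported as an answer to the primary objective.

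The Bonferroni step does not prevent this. It begins only after a difference has been found, so it cannot control the chance of finding one somewhere among the measures.

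**Working it through.** **The plan's own figure.** No error rate, power or correlation is stated. The only related figure is the recruitment target in section 9, and it reproduces: 25 / (1 − 0.15) = 29.4, rounded up to 30.

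**Number of tests (inferred; the plan gives no count).** Section 10.4 describes agents "delivered transdermally using iontophoresis to three sites" (finger, foot, forearm), with conductance measured at each: 3 measures. The cold challenge gives skin temperature and skin blood flow at hand and foot: 2 × 2 = 4. Total: 3 + 4 = 7. Two other readings are open:

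- one test for each of the three domains in section 6.1, giving 3;
- acute and chronic supplementation (section 7.1) tested separately, giving 7 × 2 = 14.

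**Formulas, with no true effect and each test at two-sided 0.05.**

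- Independent tests, a difference in either direction: 1 − 0.95^k.
- Independent tests, a false benefit only: 1 − 0.975^k.
- Tests with a common correlation ρ, either direction: 1 − E[{Φ((1.96 − √ρ·U)/√(1−ρ)) − Φ((−1.96 − √ρ·U)/√(1−ρ))}^k], with U standard normal, by numerical integration. For a false benefit, drop the second Φ term.

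With k = 7 and independence: 1 − 0.95^7 = 0.302, and 1 − 0.975^7 = 0.162.

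| Tests | Direction | ρ = 0 | ρ = 0.5 | ρ = 0.7 | ρ = 0.9 |
|---|---|---|---|---|---|
| 7 | either | 30.2% | 23.0% | 17.8% | 11.4% |
| 7 | benefit | 16.2% | 11.5% | 8.9% | 5.7% |
| 3 | either | 14.3% | 12.5% | 10.9% | 8.4% |
| 3 | benefit | 7.3% | 6.3% | 5.5% | 4.2% |
| 14 | either | 51.2% | 34.8% | 24.9% | 14.1% |

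For a single test the values are 5% in either direction and 2.5% for a benefit.

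**Check at the planned size.** Simulated paired t tests with n = 25 and seven measures gave 29.7% (ρ = 0), 23.7% (0.5) and 18.4% (0.7), in line with the normal calculation.

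**The case against.** The strongest reply is that this is openly a pilot. Leaving out a primary outcome is deliberate and disclosed, the estimation purpose is stated several times, and nothing makes the next trial depend on a P value. That stands. A reader might infer that the trial is designed to deliver an efficacy verdict on the first significant result, and the synopsis and sections 6, 6.2 and 20 do not support that. The reply does not explain why section 14 omits the promised estimates and keeps an acceptance rule that is not labelled exploratory.

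The size is also open to challenge, and much of the challenge stands.

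- The documents do not say that each measure is tested separately. Site could be a factor within one ANOVA, and the phrase about analysing sites separately in section 10.4 concerns the acetylcholine dose response.
- Section 6.1 joins its three domains with *and*. If a positive answer needs all three, error is not inflated.
- Several measures come from the same hand or foot, so correlations above 0.7 cannot be excluded.
- A reader might take 18-30% as the chance of wrongly concluding that the juice helps. It is not: it counts differences in both directions, and the false-benefit figure is about half as large.

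A reader might also infer that feasibility should become the sole basis of the trial's conclusion. Section 6.2 places feasibility among the secondary objectives, and reordering them is the sponsor's decision.

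**Conclusion.** The point holds as a mismatch between purpose and analysis: the pilot is described as estimating effects, while section 14 specifies only significance testing without control across measures.

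On the assumption of seven separate tests, the chance of at least one spurious P < 0.05 is about 18-30% in either direction for correlations of 0.7 to 0, falling to 11% at 0.9. For a spurious benefit it is about 9-16%. One test per domain lowers these to 11-14% and 5.5-7.3%. Separate acute and chronic tests raise the either-direction figure to 25-51%. Both the test count and the correlations are assumptions, because the documents give neither.

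This should be fixed, but it does not undermine the trial: the design and data are unaffected, and the estimation purpose is already on record.

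**What to change.** - **Synopsis and section 6.1:** restate the primary objective as *to estimate, with 95% CI, the CBJ-minus-placebo difference in [listed measures] after acute and after chronic supplementation*. Reword the discomfort and pain objective in section 6.2, and its copy in the synopsis, in the same form.
- **Section 14.2:** replace the P < 0.05 acceptance rule with the within-participant difference and 95% CI for every listed measure, alongside the means ± SD. State that P values are exploratory, unadjusted and not a basis for an efficacy conclusion.
- **Section 14.3:** amend the post hoc step, which is triggered by a significant result and would otherwise depend on a rule that no longer exists.
- **Leave unchanged:** the sponsor's ordering of primary and secondary objectives, and the decision not to name a primary outcome.

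The cost is wording in the synopsis and in sections 6.1, 6.2, 14.2 and 14.3, with no added participants, visits or measurements. The downside is that the pilot can no longer report significant efficacy.

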### 6.2 Secondary Objectives

Secondary objectives: 1) Does CBJ reduce perceived discomfort and pain; 2) is our protocol acceptable to individuals with RP (i.e. cold water stimulus, CBJ palatability) and feasible to perform in a future multi-centre randomised control trial (RCT); and 3) to establish recruitment and retention rates. Resulting estimated effect sizes in relation to their confidence intervals from our primary objective(s) measures will be utilised to identify our primary outcome measure and to power a larger, definitive, multi-centre randomised, control trial.

## 7. STUDY DESIGN

### 7.1 Summary of Study Design

The proposed study will be a pilot, randomised placebo-controlled, double-blind, crossover trial. The effect of acute and chronic CBJ supplementation on microvascular function in people with RP will be compared to a placebo (CBJ with the nitrates removed). The placebo is the same in colour, odour, texture and taste as CBJ (Mark [name] et al., 2014) but does not cause an increase in plasma nitrate or nitrite ([name] et al., 2016). The volunteers will be given a full briefing about the study and given the participant information sheet before we seek their written consent (see below). The individual's severity of RP symptoms will be established according to the International Consensus Criteria for Diagnosing RP (Maverakis et al., 2014).

*Participants and Recruitment:* Twenty-five individuals with RP would need to be recruited in order to estimate a moderate to large effect size in a pilot study (Johanson & Brooks, 2009). Therefore, we aim to recruit 30 individuals (at a rate of 1 per week) with RP to account for a 15% drop-out rate (typically seen in our clinical trials). Participants will be recruited from a database of known individuals with RP who attend outpatient clinics at the Queen Alexandra Hospital (Portsmouth) and via posters and word of mouth within the University of Portsmouth. The participants will attend the lab on five occasions during which cold sensitivity and endothelial function (iontophoresis) will be assessed (Spinnaker Building, University of Portsmouth).

*Consent and Screening:* Visit 1 will act as a screening, consent and baseline assessment (3.5-4 hours).

Participants will be given the opportunity to ask any questions they may have after reading the participant information sheet. A standard medical history and clinical examination will be undertaken by a research nurse or member of the research team, including for example height, mass, electrocardiogram, ankle-brachial pressure index and blood sample collection for lipids and biochemical markers, urea and electrolytes, and liver function tests. Seated resting blood pressure measurements will be performed to calculate systolic, diastolic blood pressure and cutaneous vascular conductance (flux/MAP). The participants will then undertake an endothelial function (iontophoresis) test in an ambient temperature of 23°C followed by a cold challenge in an ambient temperature of 30°C (both described below) as baseline measures. Quality of life will be examined through the provision of the Medical Outcomes Study 36-item Short Form Health Survey (SF-36). |Following this visit, a letter will be sent to their General Practitioner (GP), confirming their participation within the trial. Participants who do not want their GP informed will be provided with the GP letter.

*Randomisation:* During the first visit the participants will be randomised by a nurse to begin either the CBJ or placebo arm of the study. A computer programme will be utilised to randomly allocate to treatment order, whilst stratifying for disease type and gender. Participants will be provided with instructions and their first acute dose to take away with them.

*Visit 2 and 4 (acute supplementation visits ~ 1.5-2 hours).* One and a half hours before visits 2 and 4, participants will be instructed to ingest an acute dose of 140 ml of either CBJ (delivers ~ 12.4 mmol·L of inorganic nitrate) or placebo (~ 0.002 mmol·L Beet It, Heartbeet Ltd.). The primary objectives (peripheral blood flow, endothelial function and skin temperature; see below for details) will be assessed ~ 1.5 hours after arrival in the research facility. The timing of the supplement is key to ensure plasma / saliva nitrate and nitrite are elevated throughout the testing period (Webb et al., 2008). On arrival at the laboratory, the participants will have their BP measured and a ~ 20 ml venous blood sample taken. The participants will then undertake an endothelial function (iontophoresis) test in an ambient temperature of 23°C followed by a cold challenge in an ambient temperature of 30°C (both described below). The SF-36 will also be measured here. Visits 3 and 4 (crossover period) will be separated by at least 7 days to allow washout (Wylie et al., 2013) and all visits will be conducted at the same time of day in a counter-balanced order at a time suitable for the participants.

*Visit 3 and 5 (chronic supplementation visits ~ 1.5-2 hours).* Visits 3 and 5 will be identical in nature to visit 2 and 4, however, following chronic supplementation of 70 ml·day of either CBJ or placebo for 14 days (Vanhatalo et al., 2010; Wylie et al., 2013). With consent, participants will be reminded to take the juice via text message or voice mails. Please see the accompanying documents for the participant flow through the study.

The participants diet will be standardised prior to testing and they will be asked to abstain from using antibacterial mouth wash for 7 days prior to each test and throughout the period of testing as this has been shown to reduce the concentration of oral microflora that are responsible for the reduction of nitrate to nitrite (Govoni, Jansson, Weitzberg, & Lundberg, 2008). Participants will also be asked to refrain from using other medicines during the testing period that may affect blood flow or the release of nitrite from the CBJ with such as organic nitrates, proton pump inhibitors, ranitidine and nicorandil.

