### 11. INTERVENTIONS

#### 11.1 Description of Study Intervention / Treatment

*Visit 2 and 4 (acute supplementation visits ~ 3 hours).* One and a half hours before visits 2 and 4, participants will be instructed to ingest an acute dose of 140 ml of either CBJ (delivers ~ 12.4 mmol·L of inorganic nitrate) or placebo (~ 0.002 mmol·L Beet It, Heartbeet Ltd.). The primary objectives (peripheral blood flow, endothelial function and skin temperature; see below for details) will be assessed ~ 1.5 hours after arrival in the research facility. The timing of the supplement is key to ensure plasma nitrate and nitrite are elevated throughout the testing period (Webb et al., 2008). On arrival at the laboratory, the participants will have their BP measured and a ~ 20 ml venous blood sample taken for determination of plasma [nitrate], [nitrite] and nitrotyrosine and protein carbonyl concentrations (which are clinically relevant markers of oxidative stress (Frijhoff et al., 2015)). The participants will then undertake an endothelial function (iontophoresis) test in an ambient temperature of 23°C followed by a cold challenge in an ambient temperature of 30°C (both described below). Visits 3 and 4 (crossover period) will be separated by at least 7 days to allow washout (Wylie et al., 2013) and all visits will be conducted at the same time of day in a counter-balanced order at a time suitable for the participants.

*Visit 3 and 5 (chronic supplementation visits ~ 3 hours).* Visits 3 and 5 will be identical in nature to visit 2 and 4, however, following chronic supplementation of 70 ml·day of either CBJ or placebo for 14 days (Vanhatalo et al., 2010; Wylie et al., 2013). With consent,

participants will be reminded to take the juice via text message or voice mails. Please see the accompanying documents for the participant flow through the study.

The participants diet will be standardised prior to testing and they will be asked to abstain from using antibacterial mouth wash for 7 days prior to each test and during the testing phase as this has been shown to reduce the concentration of oral microflora that are responsible for the reduction of nitrate to nitrite (Govoni et al., 2008). Participants will also be asked to refrain from using other medicines during the testing period that may affect blood flow or the release of nitrite from the CBJ with such as organic nitrates, proton pump inhibitors, ranitidine and nicorandil.

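### Do the differing lengths for visits 2 to 5 leave the acute dose-to-test timing unsound?

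*Combined protocol and SAP*

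**What the plan says.** Section 7.1 describes visits 2 and 4 as "acute supplementation visits ~ 1.5-2 hours" and visits 3 and 5 as "chronic supplementation visits ~ 1.5-2 hours". Section 11.1, in nearly the same text, has "acute supplementation visits ~ 3 hours" and "chronic supplementation visits ~ 3 hours". Section 16.1, reporting what was put to people with Raynaud's phenomenon, speaks of five visits of three hours each.

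On dosing and testing at the acute visits, sections 7.1 and 11.1 agree with each other:

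- Dose: "One and a half hours before visits 2 and 4, participants will be instructed to ingest an acute dose of 140 ml".
- Assessment: the primary measures, endothelial function among them, "will be assessed ~ 1.5 hours after arrival in the research facility".
- Order: blood pressure and a blood sample on arrival, and then "The participants will then undertake an endothelial function (iontophoresis) test in an ambient temperature of 23°C followed by a cold challenge".

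Section 7.1 gives the reason for the care over timing: "The timing of the supplement is key to ensure plasma / saliva nitrate and nitrite are elevated throughout the testing period". Section 11.1 says the same for plasma. Both sections refer to accompanying documents for the participant flow, and Appendix 2 is the study flow chart. Neither was available for this review.

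**The concern.** Two things look wrong. First, the same four visits have two lengths in the body of the protocol, and the approximation sign cannot stretch 90 to 120 minutes to 180. Second, section 7.1 seems to contradict itself: if the first assessment comes 1.5 hours after arrival, a 1.5-hour visit would end as testing begins.

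The order of events adds to the doubt. Neither section mentions a wait between the arrival procedures and iontophoresis, yet the assessment sentence seems to imply one. The time from the acute dose to the first measurement is then uncertain, in a protocol that calls supplement timing key.

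What would be at stake is the meaning of the acute effect size. Section 6.2 uses the effect sizes to choose a primary outcome and to power a multi-centre trial, where other sites would have to reproduce the post-dose time. Loose timing between visits 2 and 4 would also add noise to a within-participant comparison.

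**Working it through.** **Inputs**

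- Iontophoresis acclimatisation: 30 min (section 10.4).
- Iontophoresis current: 8 × 20 s = 160 s = 2.67 min (section 15). If each of 3 sites × 2 agents needs its own run in sequence, 6 × 2.67 = 16 min. The second figure is an assumption; section 15 does not say.
- Cold challenge: 15 min acclimatisation + 12 min exercise = 27 min, then 2 min immersion + 10 min rewarming per limb (section 10.4). That is 12 min with hand and foot overlapped, or 24 min in sequence.
- Blood pressure and blood sample: no duration is stated; 0 to 20 min is assumed.
- Acute dose: 90 min before the visit (sections 7.1 and 11.1).

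The lower figure in each range uses one iontophoresis run and overlapped limbs; the upper uses six runs and limbs in sequence. The SF-36, probe set-up, recording between pulses and the change of room temperature are not counted, so these are minimum times.

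**Visit length under each reading of the assessment sentence**

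1. It marks the first iontophoresis measurement (acclimatisation inside the 90 min): 90 + 2.67 + 27 + 12 = 131.7 min, up to 90 + 16 + 27 + 24 = 157 min. One run with limbs in sequence gives 90 + 2.67 + 27 + 24 = 143.7 min.
2. It marks the start of iontophoresis acclimatisation: add 30 min to each, giving 161.7 to 187 min.
3. It marks the cold immersion: 90 + 12 = 102 min, or 90 + 24 = 114 min.
4. No wait (the order of events as written): 30 + 2.67 + 27 + 12 = 71.7 min with nothing for the arrival procedures, up to 20 + 30 + 16 + 27 + 24 = 117 min.

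**Time from dose to first iontophoresis measurement**

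- Reading 1: 1.5 + 1.5 = 3.0 h.
- Reading 2: 1.5 + 1.5 + 0.5 = 3.5 h.
- Reading 3: iontophoresis starts 90 − 27 − 2.67 = 60.3 min after arrival (one run) or 90 − 27 − 16 = 47 min (six runs), so (90 + 60.3)/60 = 2.5 h or (90 + 47)/60 = 2.3 h.
- Reading 4: 1.5 + 30/60 = 2.0 h, up to 1.5 + 50/60 = 2.3 h.

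| Reading | Minimum visit (min) | Within 120 min? | Dose to first test (h) |
|---|---|---|---|
| 1. First iontophoresis at 90 min | 132–157 | No, over by 12–37 | 3.0 |
| 2. Acclimatisation from 90 min | 162–187 | No, over by 42–67 | 3.5 |
| 3. Immersion at 90 min | 102–114 | Yes | 2.3–2.5 |
| 4. No wait | 72–117 | Yes | 2.0–2.3 |

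Section 7.1's visit length is thus consistent with the order of events it describes. The tension inside that section comes from one sentence, and only on readings 1 and 2. Because the totals are minimum times, they cannot show that about 3 hours is enough either; at the top of reading 2 they already exceed 180 min.

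**Effect on the comparison.** Visits 2 and 4 are covered by one description, and all visits are to be held at the same time of day. Whatever post-dose time is used in one period is, as written, used in the other, so it does not enter the within-participant difference as bias. The arrival blood sample falls about 1.5 h after the dose on every reading.

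**The case for a change.** The strongest case for acting has three parts. The visit lengths disagree on their face, with no calculation needed. The assessment sentence names endothelial function, so reading 1 is its plain meaning and reading 3 is strained. And the possible post-dose times span 2.0 to 3.5 h, a wide range for an effect size that other centres would later have to reproduce; the cure is a few words and perhaps some clock-time fields on the forms.

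The first part stands in full: sections 7.1, 11.1 and 16.1 do not agree. The second stands in part. On the plain reading the 1.5-hour figure is impossible, but the excess over 2 hours is only 12 min at the minimum, and both figures are marked as approximate. It becomes firm at about 24 min (143.7 − 120) if the limbs are tested in sequence.

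The third part shows an ambiguity in the text, not a fault in the result. The stated purpose of the timing is that nitrate and nitrite stay raised during testing, and nothing in the documents shows that a first test at 2.0, 3.0 or 3.5 h would miss that. Nor does anything suggest that the two acute visits would be timed differently from each other. Section 13.1 lists no clock times among the recorded items, but it only summarises forms that were not available, so its silence carries little weight.

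**Conclusion.** This is a minor internal inconsistency: approximate visit lengths that were not aligned across sections 7.1, 11.1 and 16.1, and one sentence that does not say which step it times. The passages must be reconciled to a single visit length, and the sentence tied to a named step, when the protocol is next edited. The timing is for the sponsor to state, and the flow chart may already do so.

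No change to the design, assessments or analysis follows. The discrepancy is 60 to 90 min in stated visit length (180 − 120 and 180 − 90) and up to 1.5 h in the possible dose-to-test interval (3.5 − 2.0), but no bias in the comparison of beetroot juice with placebo has been shown. The team running the visits has to settle on a workable schedule, and can report the post-dose time used alongside the effect size.

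This conclusion assumes that one schedule is followed in both periods, as the shared description implies. The lower end of the interval also rests on the assumed 0 to 20 min for blood pressure and blood sampling.
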